11.9 Safety Analyses

Review of safety tables, listings and figures will be performed by the medical monitor or designee. The safety tables will allow a view of changes from baseline in findings from 12-lead ECGs, vital signs, clinical laboratory values, and adverse events. No statistical testing will be executed for safety measures.

In this safety study with a limited sample size and projected high subject exclusion rate, the safety analysis will be performed on the Safety population. These analyses will include categorization of events per study phase (before and after cell infusion or assigned treatment) and event attribution as appropriate to the study phase. All analyses will include those at baseline, to 2 weeks post-index procedure.

Safety analyses will be performed on all available data through Visit 12 (Month 24) at the time of conduct of the efficacy analysis. In addition, the final safety analysis will be performed at 24 months for all patients.

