9. ASSESSMENT OF SAFETY

9.1 Safety Endpoints

All safety endpoints will be assessed from subject randomization through up to 24 months post investigational agent infusion:

- SAE / AE rates
- Occurrence of MACCE including:
 - Cardiovascular death
 - Non-fatal myocardial infarction
 - Non-fatal stroke
 - Cardiac hospitalization due to heart failure
- Target vessel (or other vessel) revascularization post index cardiac catheterization and new or worsening heart failure during the index hospitalization will be tracked as “Adverse Events of Special Interest”.
- Total number of subjects with documented ventricular arrhythmia (sustained and non-sustained VT/VF) throughout the study period.
- Angina pectoris as defined by CCS clinical clarification.
- NYHA Class.
- Telemetry/48 hour Holter monitoring (during hospital admission and at 14 and 30 days, 3 and 6 months follow-up time points) with assessment of occurrence of ventricular arrhythmia.
- TIMI flow and perfusion measurements following intracoronary infusion of the MPC cell solution compared with placebo.
- Physical examinations, monitoring of vital signs (heart rate, respiratory rate, BP, and temperature).
- Results of clinical laboratory tests (hematology, serum chemistry, inflammatory markers), and immunogenicity assays; (flow cytometry Class I and Class II HLA percent reactivity % with specificity, antibovine and antimurine antibody analysis).

AE will be collected after a subject has been randomized. The AE will be graded according to the protocol as “mild”, “moderate”, “severe” and will be classified according to MedDRA.

An independent DSMB will review all safety and relevant clinical data at regular intervals in accordance with their charter. Based on its findings, the DSMB will make recommendations regarding study continuation, enrollment and/or study modification(s).

The primary safety analysis will be performed on the following safety and feasibility parameters up to 30 days post-treatment:

- TIMI flow prior to, during (approximately 50% of total infusion of investigational agent) and following infusion of investigational agent after successful PCI.
- SAE/AE rates.
- Results of clinical laboratory tests (including hematology, serum chemistry, inflammatory markers, flow cytometry anti-HLA Class I and Class II percent reactivity with specificity, antibovine and antimurine antibody analysis).
- Infusion procedure monitoring of vital signs (heart rate, respiratory rate, BP, and temperature).

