11.3 General Considerations

All clinical test results will be listed and summarized by treatment and time with appropriate descriptive statistics (number of observations, mean, median, standard deviation, minimum, and maximum) for continuous measures. Nominal and ordinal scale measures will be summarized with frequency tables, relative risk, and percentages, as appropriate.

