11.8 Efficacy and Feasibility Analyses

Where appropriate, 95% confidence intervals for treatment differences in key feasibility measures will be constructed. Analysis of covariance (ANCOVA) may be used where appropriate to adjust for baseline differences in key continuous feasibility outcome measures and also take the site and the time from onset of AMI symptoms to PCI as covariates in the ANCOVA model. For non-normally distributed measures, the Wilcox-Mann-Whitney test or analysis of variance ANOVA of rank transformed data may be used as an alternative. For categorical measures, relative risks and nominal 95% confidence intervals will be constructed to assess strength of association. The Cochran-Mantel-Haeszel test (CMH) controlled by site and the time from the onset of AMI symptom to PCI will be used for the treatment differences. The primary feasibility analysis will be performed on the FA population, and confirmatory based on PP population.

The primary and secondary efficacy analyses will be performed on ITT, FA, and PP populations. Analysis of clinical endpoints will be performed on all analysis populations.

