11.10 Timing of Planned Analyses

Primary and Secondary Efficacy Analysis:

Analysis of efficacy will occur once all subjects have completed the 6-month visit.

Feasibility analysis:

Feasibility analysis based on TIMI flow will be concurrent with the analysis of efficacy described above.

Initial Safety Follow Up:

Preliminary analysis of safety will be concurrent with the analysis of efficacy described above.

Long Term Safety Follow up:

Analysis of long-term safety will occur once all subjects have completed the 24-month visit.

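### At the Month 6 readout, cumulative MACCE and later adverse events would be pooled over about 6 to 24 months of follow-up, so the percentages would estimate neither 6-month nor 24-month risk

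*Combined protocol and SAP*

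**What the plan says.** - **Trigger.** Section 11.10: "Analysis of efficacy will occur once all subjects have completed the 6-month visit". For safety at that point it adds: "Preliminary analysis of safety will be concurrent with the analysis of efficacy described above".
- **Data included.** Section 11.9: "Safety analyses will be performed on all available data through Visit 12 (Month 24) at the time of conduct of the efficacy analysis". The synopsis and section 11.2 say the same. A final safety analysis follows at 24 months for all patients.
- **Endpoint window.** Section 9.1: "All safety endpoints will be assessed from subject randomization through up to 24 months post investigational agent infusion".
- **Summary measures.** Section 11.3: "Nominal and ordinal scale measures will be summarized with frequency tables, relative risk, and percentages, as appropriate". Section 11.8, on efficacy and feasibility, adds: "For categorical measures, relative risks and nominal 95% confidence intervals will be constructed to assess strength of association". It also sends the clinical endpoints, which include MACCE (section 8.3), to all analysis populations.
- **Fixed windows.** Section 9.1: "The primary safety analysis will be performed on the following safety and feasibility parameters up to 30 days post-treatment". That list includes SAE/AE rates but does not name the MACCE composite. Section 11.9 separately mentions a period from baseline to 2 weeks after the index procedure. In section 4.3 the DSMB reviews MACCE frequency once set numbers of subjects have been observed at Day 30.

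The text contains no Kaplan-Meier or cumulative incidence estimate, no event rate per unit of person-time, and no rule cutting each subject's data at a common follow-up time.

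**The concern.** Safety is part of the primary objective (section 4.1), MACCE is the adjudicated safety composite (section 5.4.3), and the Month 6 report is the first planned unblinded readout. At that cut the last subject has about 6 months of observation and the earliest may have the full 24. A simple percentage over such a mixture averages the cumulative risk curve over whatever follow-up times enrolment happened to produce. The same event process gives a higher figure if enrolment was slow and a lower one if it was fast. That figure cannot be set beside the 24-month report or another study's 6-month risk, and a reader is likely to take it for the 6-month risk and overstate it.

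**Working it through.** **No planned figure to reproduce.** The documents give neither a MACCE or AE rate nor an accrual period. What follows is an illustration on stated assumptions.

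**Inputs from the plan.** Analysis when the last subject reaches 6 months (section 11.10); follow-up capped at 24 months (sections 9.1 and 11.9).

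**Assumed.** Even accrual over A = 12, 24 or 36 months; one-year risk p = 5%, 10% or 20%; no dropout; two hazard shapes.

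**Formula.** A subject enrolled u months before the last one has follow-up min(24, 6 + u). With F(t) the cumulative risk at t months, the expected pooled proportion is (1/A) × ∫ F(min(24, 6 + u)) du over u from 0 to A. For A = 24 this is [∫ F(t) dt from 6 to 24, plus 6 × F(24)] / 24, and mean follow-up is (18 × 15 + 6 × 24)/24 = 17.25 months.

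**Constant hazard, p = 10%, A = 24.**
- λ = −ln(0.9)/12 = 0.00878 per month.
- Integral of survival from 6 to 24: (0.9487 − 0.8100)/0.00878 = 15.80.
- Mean survival: (15.80 + 6 × 0.81)/24 = 0.8606, so the pooled proportion is 13.9%.
- Risk at fixed times: 5.1% at 6 months, 10.0% at 12, 19.0% at 24. Ratio to the 6-month risk: 2.7.

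**Front-loaded risk (Weibull shape 0.5), same p and A.**
- F(t) = 1 − exp(−0.1054 × (t/12)^0.5).
- Integral of F from 6 to 24: 1.966; F(24) = 0.1384.
- Pooled: (1.966 + 6 × 0.1384)/24 = 11.7%.
- Risk at fixed times: 7.2% at 6 months, 13.8% at 24. Ratio: 1.6.

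**Full grid** (pooled percentage, with its ratio to the 6-month risk):

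| One-year risk | Hazard | 6-month risk | A = 12 | A = 24 | A = 36 |
|---|---|---|---|---|---|
| 5% | constant | 2.5% | 5.0% (1.97) | 7.1% (2.80) | 8.0% (3.15) |
| 10% | constant | 5.1% | 10.0% (1.94) | 13.9% (2.72) | 15.6% (3.05) |
| 20% | constant | 10.6% | 19.8% (1.88) | 27.0% (2.56) | 30.0% (2.84) |
| 5% | front-loaded | 3.6% | 4.9% (1.39) | 5.9% (1.65) | 6.2% (1.75) |
| 10% | front-loaded | 7.2% | 9.9% (1.38) | 11.7% (1.62) | 12.4% (1.73) |
| 20% | front-loaded | 14.6% | 19.8% (1.35) | 23.0% (1.58) | 24.4% (1.67) |

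Within each row the event process is fixed and only enrolment time changes. An estimate at a fixed 6-month horizon would target the third column whatever the accrual.

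**Dropout in the final analysis.** At the roughly 4% in section 11.5, 0.04 × 35 = 1.4 subjects per arm would have incomplete data.

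**The case against.** **The plan does have fixed windows.** A reader might infer that no reported event rate belongs to a defined time. That goes too far. Section 9.1 gives SAE/AE rates a 30-day primary window, and every retained subject is past Day 30 when the last completes Month 6. The final analysis has a 24-month horizon, and the DSMB's MACCE reviews are tied to Day 30. What remains is the all-available-data summary at Month 6, which has no time reference. MACCE is the clearest case, because the composite is not named in the 30-day list.

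**Simple percentages are an inference.** Section 11.9 itself prescribes no summary measure for events, section 11.3 is qualified by appropriateness, and section 11.2 refers to an SAP to be finalised before any analysis. Section 11.3 also says: "All clinical test results will be listed and summarized by treatment and time with appropriate descriptive statistics", but that sentence concerns test results, not cumulative event counts. Simple percentages are the natural reading of the only methods written, but the firm statement is that no method accounting for follow-up is specified.

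**The comparison between arms is sound.** A reader might suspect that the data cut favours one arm. With concurrent 1:1:1 randomisation expected follow-up is the same in each, so there is no systematic bias unless dropout differs by arm. Section 11.9 also excludes statistical testing of safety.

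**The final analysis is not equally affected.** The dropout figure is small, and section 5.3 allows telephone safety follow-up to 24 months after withdrawal unless the subject refuses. The documents do not say whether 4% also applies at 24 months.

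**Constant hazard exaggerates the gap.** This stands. The background in section 2.1 describes risk concentrated in the first month after infarction. Front-loaded risk brings the ratio down to about 1.35 to 1.75, so the constant-hazard ratios should not be quoted alone. The gap shrinks but does not close.

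**Conclusion.** The point holds for the preliminary safety report at Month 6. As written, cumulative MACCE, and adverse events counted beyond 30 days, would be pooled over roughly 6 to 24 months of follow-up (less for subjects who die or drop out). The result would estimate neither 6-month nor 24-month risk. In the illustration it exceeds the 6-month risk by a factor of about 1.35 to 3.15, depending on hazard shape, accrual time and event rate, all of which are assumptions. What suffers is the meaning of the absolute risks. The documents do not support a claim of systematic bias between arms, of undefined 30-day SAE/AE rates, or of more than a slight effect on the final 24-month analysis. It should be corrected before the Month 6 unblinding, so that the method is not chosen with results in view.

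**What to change.** In section 11.9, and in the SAP before the Month 6 unblinding:

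1. Report MACCE, death and adverse events of special interest by arm as Kaplan-Meier or cumulative incidence estimates, with non-cardiovascular death competing for MACCE. Give them at Day 30 and Month 6, and at Month 24 in the final report, with 95% confidence intervals and numbers at risk. This is estimation, so it is compatible with the exclusion of safety testing.
2. Cut the main Month 6 safety tables at each subject's Month 6 visit.
3. Show data beyond that visit in a separate table, with adverse events per unit of person-time.
4. Reconcile the 2-week period in section 11.9 with the 30-day primary safety window in section 9.1.

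No new visits or subjects are needed. The work is plan wording and standard programming, provided event dates are among the details that section 9.7 requires on the eCRF. The downside is slightly more analysis and a separate table for later data.

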11.10 Timing of Planned Analyses

Primary and Secondary Efficacy Analysis:

Analysis of efficacy will occur once all subjects have completed the 6-month visit.

Feasibility analysis:

Feasibility analysis based on TIMI flow will be concurrent with the analysis of efficacy described above.

Initial Safety Follow Up:

Preliminary analysis of safety will be concurrent with the analysis of efficacy described above.

Long Term Safety Follow up:

Analysis of long-term safety will occur once all subjects have completed the 24-month visit.

12. QUALITY CONTROL AND QUALITY ASSURANCE

The Sponsor shall implement and maintain quality control and quality assurance procedures with written standard operating procedures to ensure that the study is conducted and data are generated, documented, and reported in compliance with the protocol, GCP, and applicable regulatory requirements. This study shall be conducted in accordance with the provisions of the Declaration of Helsinki (October 1996) and all revisions thereof, and in accordance with applicable regulations and with the ICH guidelines on GCP (ICH E6).

13. REGULATORY OBLIGATIONS

13.1 Institutional Review Board (IRB)/ Ethics Committee (EC) Approval

Prior to enrollment of subjects into the study, as required by relevant regulations, the protocol, and informed consent form will be reviewed and approved by an appropriate IRB/EC. By signing the Statement of Investigator Form (FDA 1572 or equivalent), the investigator assures that all aspects of the institutional review will be conducted in accordance with current federal regulations and ICH. A letter documenting the IRB/EC approval must be received by the sponsor prior to the initiation of the study. Amendments to the protocol will be subject to the same review and approval requirements as the original protocol.

The investigator shall promptly notify the IRB/EC of any SAE, or any other information that may affect the safe use of the drug during the course of the study.

13.2 Protocol Compliance

Except for a change that is intended to eliminate an apparent immediate hazard to a study subject, the protocol shall be conducted as described. Protocol violations must be reported immediately to the Sponsor or its representative(s) as well as the governing IRB/EC and relevant regulatory authority as required.

13.3 Changes to the Protocol

The investigator may not deviate from the protocol without a formal protocol amendment having been established and approved by an appropriate IRB/EC, and relevant regulatory authority if required, except when necessary to eliminate immediate hazards to the subject or when the change(s) involve only logistical or administrative aspects of the study. Any deviation may result in the subject having to be withdrawn from the study and rendering that subject non-evaluable.

13.4 Informed Consent

Each subject must sign the study-specific informed consent form to enroll as a participant in the study. This consent form will comply with all applicable regulations governing the protection of human subjects. The basic elements of informed consent are specified in the ICH Guideline for GCP (E6).

13.5 Source Documents

During the study, the investigator will maintain adequate records for the study, including medical records, records detailing the progress of the study for each subject, laboratory reports, study worksheets/subject questionnaires, signed informed consent forms, drug disposition records, correspondence with the IRB/EC/Competent Authority, AE reports, and information regarding subject discontinuation and completion of the study.

13.6 Case Report Form Completion

All data obtained during this study should be entered on the eCRFs promptly. All source documents from which eCRF entries are derived should be placed in the subject's medical records.

13.7 Financial Disclosures

In accordance with the US Code of Federal regulations, Title 21, Part 54, the investigator will provide the Sponsor or its designee sufficient and accurate information on financial interests (proprietary or equity interests, payments exclusive of clinical study costs) to allow complete disclosure to regulatory authorities. The investigator shall promptly update this information with any relevant changes that occur during the course of the study and for a period of 1 year following the completion of the study.

13.8 Termination of the Study

If the Investigator, Medical Monitor, ESC or DSMB becomes aware of conditions or events that suggest a possible study related hazard to subjects if the study continues, they may recommend to the Sponsor that the study be terminated after appropriate consultation between the relevant parties. The decision to terminate the study remains with the Sponsor. The study may also be terminated early at the Sponsor's discretion in the absence of such a finding.

Conditions that may warrant termination by the Sponsor may include, but are not limited to:

- The discovery that in the opinion of the Sponsor poses an unexpected, significant, or unacceptable risk to the subjects enrolled in the study;
- A decision on the part of the Sponsor to suspend or discontinue development of the test material for any reason.

13.9 Retention of Essential Documents

All records and documents pertaining to the study including, but not limited to, those outlined above will be maintained by the investigator for at least a period of (or longer depending upon the local Regulatory Agency requirements): (a) 2 years after last approval of the product; (b) 5 years after non-approval of the Biologics License Application (BLA); or (c) 2 years after termination of investigational agent development program. In order to avoid any possible errors, the investigator will contact the Sponsor prior to the destruction of any study records. The investigator will promptly notify the Sponsor in the event of accidental loss or destruction of any study records.

13.10 Confidentiality

All study findings and documents will be regarded as confidential. The investigator and members of his/her research team must not disclose such information without prior written approval from the Sponsor.

